7.4 Sensitivity Analyses of the Primary Outcome

Additional analyses of the primary outcome may include, but are not limited to:

- (a) An analysis of global cognitive function in which data from in-person cognitive evaluations will be stratified by condition before a factor score is computed for each participant. The factor scores generated will be standardized using the condition-specific baseline mean and SD.
- (b) An analysis of a co-calibrated^{23,24} global cognitive function factor score in which the ten tests administered in-person and the six tests administered over the phone will be included in the confirmatory factor analysis model. Modeling constraints will be applied to scale the co-calibrated factor score to the same metric as the in-person factor score utilized in the primary analysis²⁵. Mode of data collection (in-person, phone) will be included in the analytic model as a covariate.
- (c) Use of full-information maximum likelihood to account for missing data. Parameter estimates from these analyses will be compared to estimates from multiple imputation analyses to gauge the impact of including auxiliary variables in the imputation model.
- (d) Control-based multiple imputation, in which missing values of the primary outcome for the hearing aid condition without a dementia diagnosis are imputed based on the successful aging control intervention condition. This analysis will investigate the strength of the primary analysis results to the missing at random assumption.

- (e) Analysis of cognitive decline based on a categorized version of time (visits) rather than continuous time in years.
- (f) A replication of the primary analyses stratified by subgroups of ARIC vs de novo participants. Interaction between intervention condition and recruitment group will be tested in additional models relative to p < 0.10.
- (g) Exploration of the impact on the primary analysis by further adjustment for additional explanatory variables, as mentioned in section 7.1.

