## 12 Statistical considerations

### 12.1 Sample size

**Aim 1:** Comparison of hearing rehabilitative intervention versus successful aging control intervention for 3-year cognitive decline

Our sample size calculation is based on the primary outcome, the change in the Global Cognitive Function Factor Score from baseline to year 3. Estimates are based on the rate of change in the global cognitive function factor score from the first third of participants in the ongoing ARIC Visit 6 study (2016 to 2017) in addition to data from other representative studies with similar cohort characteristics as ARIC/ACHIEVE (i.e., ACTIVE and HealthABC). We also take into account assumptions regarding the rate of loss to follow-up as well as the rate of cross-over, where participants in the successful aging control group begin to wear hearing aids and participants in the hearing intervention group stop wearing the devices.

We based these calculations on a t-test comparing groups on change from baseline at 3 years to align with the primary analysis (a mixed effects model treating time as categorical) and aimed to achieve 90% power using a 2-sided test with a  $p=0.05$  significance level. We conservatively chose parameter estimates that fell within the mid-range of observed values from these studies.

Parameter assumptions include:

- Change in global cognitive function factor score in the control group per year:  
Estimated at -0.08 standard deviations (SD)/year (corresponding to -0.24 SD in 3 years)
- Standard deviation of change in global cognitive function factor score per year:  
Estimated at 0.09 (corresponding to 0.27 at 3 years)
- Drop-in/Drop-out: Estimated as a net total of 15% (drop-in + drop-out) for the 3-year study. This value is conservative. We assumed immediate drop-in/drop-out rather than later drop-in/drop-out (i.e., 1-2 years into the study) which would have less impact on reducing the observed effect size. We will continue to optimize the design to keep both

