drop-in and drop-out rates low (e.g., rigorous training for active group vs. energized successful aging group promised free hearing aids at trial completion). Among 13 participants in the ACHIEVE-Pilot study who were randomized to the hearing intervention and have since been followed to 1 year, we did not observe any drop-out (discontinuation of hearing aid use) at 1 year (12 participants reported > 8 hours of hearing aid use/day and 1 participant reported 4-8 hours use/day). Similarly, drop-in rates will likely be minimized because all participants in the successful aging group are informed that they will receive free hearing intervention after 3 years of follow-up (out-of-pocket costs for hearing aids are otherwise currently ~\$4700 and are rarely covered by insurance). Rates of uptake of hearing aid use remain low in the community. In the HealthABC study among individuals with hearing loss in the inclusion range for the ACHIEVE study, rates of hearing aid uptake were ~3-4% per year.

- Missing data/withdrawal from competing events (e.g., mortality not associated with dementia): Estimated at 10%/year (corresponding to 27% in 3 years)

Based on these parameters and with 850 total individuals randomized, we will have 90% power to detect a 35% difference in annual cognitive decline between the hearing intervention vs successful aging intervention at 3 years follow-up.

**Aim 2:** For the secondary outcome of incident cognitive impairment, a dataset was constructed of participants in the ARIC cohort who had comparable characteristics to the individuals enrolled in ACHIEVE, did not exhibit signs of cognitive impairment at the baseline, and who were monitored over a period of 5 to 8 years. The observed rate was 50 cases of incident cognitive impairment per 1000 person-years. Assuming a 30% reduction in the hearing intervention condition and a 25% loss of person-time due to attrition, the planned analysis would have 80% power to detect a hazard ratio of 0.54 when using a 2-sided test and  $p < 0.05$ .

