5.1 Preliminary Analysis

Data from the ARIC cohort, the Advanced Cognitive Training for Independent and Vital Elderly (ACTIVE) randomized trial, and the Health Aging and Body Composition (HealthABC) study were utilized to estimate that in the absence of an intervention a factor score (described in section 8.0) of global cognitive function would decline at a rate of 0.08 standard deviations (SDs) per year with a variability of 0.09 SDs. These estimates of the slope and variance were translated into expected values at Year 3. Power was conservatively estimated using a simplified t-test approach, while recognizing that greater power would be provided in the analysis of the primary outcome of cognitive decline through the application of repeated measures mixed effects models (described in section 7.3). The original sample size for ACHIEVE was 850, which provided greater than 90% power to detect a 35% difference in annual cognitive decline (Intervention: -0.052, Control: -0.08) with a 2-sided test and p < 0.05.

Attrition due to withdrawal or mortality was estimated at 10% per year, corresponding to 27.1% over 3 years. This is a conservative estimate given that *total* attrition in ACHIEVE is 6.7% as of October 6th, 2021. The drop-in/drop-out rate was estimated at 15% over 3 years. This rate reflects participants in the successful aging control condition who begin to wear hearing aids (drop-in) and participants in the hearing intervention condition who stop wearing hearing aids (drop-out). As of October 6th, 2021 there are 46 participants in the control condition who are currently using hearing aids (9.4% drop-in) and 8 participants in the intervention condition who are not currently using hearing aids (1.6% drop-out). After accounting for a 15% drop-in/drop-out rate, the difference at Year 3 was reduced to 29% (Intervention: -0.057, Control: -0.08). With an attrition rate of 10% per year, the initial sample size for ACHIEVE provided greater than 80% power to detect a difference utilizing a 2-sided t-test and p < 0.05.

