7.7 Adjustment for Multiple Comparisons

Statistical significance for the primary outcome will be defined as p < 0.05. Secondary outcomes will be evaluated for statistical significance with a Hochberg modification to the Bonferroni adjustment, in which the p-values of the five outcomes will be ordered. The largest p-value will be compared relative to p < 0.05, and if met, all parameters will be considered significant. If not, then the second largest p-value will be assessed relative to p < 0.05/2 = 0.025, and if met then it and all other parameters will be considered significant, and so on for the 3rd p-value compared at 0.05/3=0.017, the fourth compared to 0.05/4 = 0.012, and the fifth compared to 0.05/5 = 0.01.

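### Optional sensitivity analysis (a) scores and scales the cognitive factor separately in each arm, so chance differences in baseline SD become slope differences that its standard error ignores

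*SAP*

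**What the plan says.** SAP 7.2 puts the primary score on one metric. Loadings come from the ACHIEVE baseline, the baseline mean is fixed at 0 and the SD at 1 for everyone, and these parameters are carried forward to later visits. SAP 7.3 tests the treatment-by-time interaction on that score.

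Sensitivity analysis (a), in SAP 7.4 and repeated in Protocol 12.2, departs from this. The in-person data are divided by arm before any score is computed, and then: "The factor scores generated will be standardized using the condition-specific baseline mean and SD". Nothing returns the two arms to a shared scale. By contrast, sensitivity analysis (b) and exploratory analysis (e) on auditory tests (SAP 7.6) both specify model constraints that keep the primary metric.

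No separate test is given for (a), so the primary interaction test is the natural reading. The list containing (a) is introduced as analyses that may be done. SAP 7.7 gives significance rules for the primary and secondary outcomes only; for the primary, "Statistical significance for the primary outcome will be defined as p < 0.05".

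**The concern.** Protocol 8 places randomisation at the end of the baseline visit. The true baseline SD and loadings are therefore the same in both arms, and any observed difference is sampling error. Arm-specific scaling uses that error as a unit of measurement. An arm whose baseline SD happens to be 4% smaller shows a decline about 4% steeper in its own units. Because both arms are expected to decline, the two slopes differ even when the intervention does nothing. A model that takes the scaled scores as data treats the two SDs as known constants, so its interval is too narrow.

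What is at stake is the usefulness of (a) as a robustness check. Disagreement with the primary result could be scaling noise, and agreement is weaker evidence than it appears. Centring on the arm mean is harmless, since it does not change slopes; the arm-specific SD and loadings are what matter.

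**Working it through.** **Inputs**
- Decline, taken as common to both arms under the null: "Estimated at -0.08 standard deviations (SD)/year (corresponding to -0.24 SD in 3 years" (Protocol 12.1), so mu = 0.24.
- SD of change: "Estimated at 0.09 (corresponding to 0.27 at 3 years" (Protocol 12.1), so sd = 0.27.
- Test: two-sided 5%, "with a 2-sided test and p < 0.05" (SAP 5.1).
- Attrition: "Estimated at 10%/year (corresponding to 27% in 3 years" (Protocol 12.1), so retained fraction k = 0.73. SAP 5.1 reports 6.7% as of October 2021, so k = 0.933.
- Crossover: "Estimated as a net total of 15% (drop-in + drop-out) for the 3-year study" (Protocol 12.1).
- Size: 850 planned (425 per arm); 977 enrolled 1:1 (about 488 per arm).
- Planned difference: -0.052 against -0.08 per year (SAP 5.1), that is 0.028 per year or 0.084 over 3 years.

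**Step 1: reproduce the plan's power.** Protocol 12.1 states "with 850 total individuals randomized, we will have 90% power to detect a 35% difference in annual cognitive decline".
- Diluted effect: 0.35 x 0.24 x 0.85 = 0.0714.
- Completers per arm: 425 x 0.73 = 310.
- SE = 0.27 x sqrt(2/310) = 0.0217, and 0.0714/0.0217 = 3.29.
- Power = Phi(3.29 - 1.96) = 90.9%.

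The stated 90% reproduces. With 977 participants the same calculation gives 94.2%, in line with the claim of more than 90% in SAP 5.2. The inputs are therefore being read as the plan uses them.

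**Step 2: size of the chance shift.** For roughly normal scores, an arm's baseline SD has relative variance 1/(2n). The log ratio of two arm SDs has variance 1/n, so its SE at 488 per arm is sqrt(1/488) = 0.045.
- Per year: 0.045 x 0.08 = 0.0036 SD, and 0.0036/0.028 = 13%.
- Over 3 years: 0.045 x 0.24 = 0.011 SD, and 0.011/0.084 = 13%.

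**Step 3: type I error under the null.**
- Variance the test allows for: 2 x sd^2/(k x n).
- Variance added by arm-specific scaling: mu^2/n.
- Ratio of true to nominal variance: 1 + k x mu^2/(2 x sd^2). The n cancels.
- True alpha = 2 x (1 - Phi(1.96/sqrt(ratio))).

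With k = 1, the ratio is 1 + 0.0576/(2 x 0.0729) = 1.395, and 1.96/sqrt(1.395) = 1.66, so alpha = 9.7%.

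| Decline | SD of change | Attrition | Ratio | True alpha |
|---|---|---|---|---|
| 0.24 | 0.27 | none | 1.395 | 9.7% |
| 0.24 | 0.27 | 6.7% | 1.369 | 9.4% |
| 0.24 | 0.27 | 27% | 1.288 | 8.4% |
| 0.24 | 0.40 (assumed) | none / 27% | 1.180 / 1.131 | 7.1% / 6.5% |
| 0.24 | 0.50 (assumed) | none / 27% | 1.115 / 1.084 | 6.4% / 6.0% |
| 0.12 (assumed) | 0.27 | none / 27% | 1.099 / 1.072 | 6.2% / 5.8% |
| 0 | any | any | 1 | 5.0% |

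The larger SDs of change are assumptions, but not remote ones. The pilot in Protocol 2.2 (40 participants) reports SDs of 0.42 and 0.39 for 6-month change in global function.

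**Step 4: simulation checks, no treatment effect.**
- t-test on 3-year change, SD of change 0.27, 425 or 488 per arm: arm-specific scaling rejects 9.6-10.0% without attrition and 7.8-8.3% with 27% attrition. Pooled scaling over the settings run gives 4.7-5.5%.
- Ten-test one-factor model refitted and standardised within each arm, 488 per arm: 7.9-9.1% at an SD of change of 0.27, and 6.6% at 0.43. The pooled factor model gives 4.5-5.3%.
- Per-person slopes over visits at 0-3 years, 488 per arm, decline 0.08 per year, with assumed intercept SD 0.9 and slope SD 0.05: 6.9% if the residual SD is 0.30 and 9.6% if it is 0.18.

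**The case against.** The strongest reply is that nothing confirmatory rests on (a). It is optional, has no threshold or decision rule, and sits beside a primary analysis on a single metric. That stands. A reader might infer that the trial's primary type I error is inflated; SAP 7.2 and 7.7 do not support that.

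Second, the size is conditional. It shrinks with noisier change or slower decline and vanishes with no decline. This also stands, and 8-10% should always be quoted with its inputs. A reader might extrapolate to a steeper decline, where the rate passes 12%, but neither document plans for more than 0.08 SD/year.

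Third, a reader might suppose that a smaller trial or heavier attrition makes matters worse. The ratio does not contain n, and attrition lowers the inflation because the baseline SD is estimated from everyone randomised. Nor do the checks show that estimating loadings by arm adds error beyond the SD scaling: the arm-wise factor model gave rates no higher than scaling alone.

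Fourth, the shift is modest. With a residual SD of 0.30, 0.0036 is about 37% of a slope SE of 0.0097, and in that setting the z-statistics from (a) and from pooled scaling correlate at 0.93. On the plan's own inputs, however, the scaling error is sqrt(0.395) = 63% of the nominal SE without attrition, which is not negligible.

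Finally, pooled scoring alone would turn (a) into a repeat of the primary analysis. This is a fair criticism of a bare instruction to pool, and the fix has to say what (a) is then for.

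**Conclusion.** The point holds for (a) as written. Arm-specific scoring and standardisation produce chance slope differences that the interaction test's standard error omits. Type I error is 8.4-9.7% on the plan's inputs, 6.0-7.1% at an SD of change of 0.40-0.50, 5.8-6.2% at half the decline, and 5% with no decline.

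This rests on three assumptions: (a) uses the primary interaction test, the arm SDs are treated as fixed, and baseline scores are roughly normal. The closed form is for a two-group comparison of 3-year change; the slope simulation suggests that a longitudinal model behaves in the same way.

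The consequence is confined to (a), which cannot serve as a clean robustness check. It is worth correcting because the correction is cheap, not because the primary result is at risk.

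**What to change.** Amend item (a) in both SAP 7.4 and Protocol 12.2.

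1. State its purpose as a check of measurement invariance: fit the factor model by arm and compare loadings and intercepts between arms, with the criterion for non-invariance named in advance.
2. Make any treatment comparison under (a) on one metric: the pooled ACHIEVE baseline mean and SD, with parameters linked to the primary metric by constraints as in (b).
3. If arm-specific scoring and scaling are kept for a treatment comparison, bootstrap participants (couples as units) through the whole scoring, scaling and model-fitting sequence, so that the interval includes the scaling error. This should bring the error rate back to about 5%. Report the two arm SDs alongside.

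The cost is a wording change in each document, an invariance criterion to agree, and some extra factor-analysis work. The bootstrap, if chosen, adds computing time because it has to be combined with the multiple imputation. The pooled-metric comparison will largely repeat the primary result. The primary analysis does not change.

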**Session B** occurs approximately 1-3 weeks after hearing aid fitting in order to allow for acclimatization to occur. If modifications are needed to the hearing aid fitting, they can occur and be documented in this or any subsequent sessions. During Session B, informal assessment of progress toward goals will be determined and needs for various hearing assistive technologies (HATs) will be assessed. HATs provide a more direct coupling of the sound source to the hearing aid, minimizing the negative effects of distance and background noise. Additional materials to support self-management are provided.

**Session C** occurs approximately 1-3 weeks after Session B. Short-term hearing aid outcomes are assessed and individually selected HATs are dispensed. Each participant will receive at least one HAT, depending on his or her specific goals, and outcomes of hearing aid use. These HATs may include the following or generally equivalent devices: Phonak ComPilot II (streaming device); Phonak ComPilot Air II (streaming device); Phonak TVLink II; Phonak clip-on mic; and/or the Phonak Roger System. Systematic orientation to HAT use is provided and additional self-management tools are dispensed.

**Session D** occurs approximately 1-3 weeks after Session C. Short-term outcomes of the comprehensive intervention approach, including use of hearing aids, HATs, and development of self-management skills, are assessed. Additional materials as needed to support self-management are provided as well as a supply of batteries.

**Booster Intervention/Interim Visits:** Scheduled semi-annual visits will capture audiologic outcomes and verify that hearing aids and HATs are functioning properly. Re-instruction in use of devices and hearing rehabilitative strategies will be provided during these visits. Booster sessions may be offered in a group format to allow for group rehabilitation for participants who are interested. We anticipate that unscheduled interim visits may also be required periodically (e.g., hearing aid malfunction), and these visits to trouble-shoot and/or repair malfunctioning hearing aids and/or HATs will be scheduled as needed if the issue cannot be resolved through a telephone conversation.

Full details of the hearing intervention can be found in the MOP.

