### **19.2.2 CERAD recall**

An oral 10-item word list memory measure (CERAD, The Consortium to Establish a Registry for Alzheimer's Disease) test is used in lieu of the visual Delayed Word Recall test (see section 7.2.4).

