At the outset of the study, an in-clinic neurocognitive assessment comprised of ten tests (see table 7.1) was administered. The assessment included the delayed word recall (exposure and recall)⁸ logical memory test (I and II)⁹, incidental learning test¹⁰, word fluency test (letters F, A, and S)¹¹, animal naming test¹¹, Boston naming test¹², digit symbol substitution⁹, trail making tests parts A and B¹³, and the digit span backwards⁹. All ten tests were used to compute a global cognitive function factor score (described in section 8.0) for each participant¹⁴ that was standardized to the baseline of the study.

Due to the outbreak of COVID-19 (see section 9.0 for details), a modified six-test phone-based neurocognitive assessment was administered beginning in July 2020. The assessment included the Consortium to Establish a Registry for Alzheimer's Disease (CERAD) word list (immediate and delayed)¹⁵

an abbreviated version of the word fluency test (letters F and A), the animal naming test, oral versions of trail making tests parts A and B, and the digit span backwards. The six tests were utilized to compute a phone-based global cognitive function factor score.

In-person administration of the original ten tests resumed in June 2021. All ACHIEVE participants will be invited to complete an in-person assessment even if the target date for the 36-month follow-up has passed. If a participant does not complete an in-person assessment, an in-person global cognitive function factor score will be imputed (see section 7.3).

ACHIEVE in-clinic test order ¹	ACHIEVE telephone test order ¹
Ensuring Speech Understanding	Ensuring Speech Understanding for Telephone
Mini Mental State Exam (MMSE)	MMSE / CDR - Participant Hybrid for Telephone ²
Delayed Word Recall - Exposure	CERAD Immediate ³
Digit Symbol Substitution	Digit Span Backward
Delayed Word Recall	CERAD Delayed ³
Incidental Learning	Oral Trails A ²
Word Fluency (FAS)	Oral Trails B ²
Animal Naming	Word Fluency (FA)
Logical Memory I	Animal Naming
Digit Span Backwards	
Trails A	
Trails B	
Boston Naming	
Logical Memory II	

 Table 7.1. ACHIEVE Neurocognitive Test Battery Components

¹Test order changes across modes of administration to enable timing delays for memory tests.

²Modification applied to the in-clinic version of the neurocognitive test for telephone administration.

³Indicates neurocognitive test not included in the original 10-test battery.

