7.2 Primary Outcome

The primary outcome is cognitive decline, as measured by the change in a global cognitive function factor score. The factor score is derived from a confirmatory factor analysis model that identifies common covariation among all cognitive tests administered in-person. Factor scores are generated for each participant at each in-person assessment using a measure harmonization and item banking approach^{16, 17}. Factor loadings and latent means for each neurocognitive test are estimated using data from the ACHIEVE baseline. The mean of the global cognitive function factor score at the baseline is set to 0 and the SD is set to 1. Fixed parameter estimates from the baseline model are then integrated into models that estimate the factor mean and SD at each subsequent assessment. This process ensures that changes over time represent changes in the underlying factor rather than changes in the scaling or meaning of the constructs. The assumption of longitudinal measurement invariance is supported by prior studies that utilized similar neurocognitive tests^{18, 19}. A final fixed parameter model analyzes available data collected in-person and

computes a global cognitive function factor score for each participant at every assessment in which one or more neurocognitive tests were completed. A comparable process is used to generate factor scores for the cognitive domains of memory, executive functioning, and language.

7.3 **Primary Analysis**

We will examine cognitive decline within each condition using mixed effects models that account for the correlation among repeated measures as well as the correlation between spouses or cohabitating partners. If a linear trend appears reasonable, we will fit a model with a linear slope. If a nonlinear trend is observed, the model will be adapted to include time splines²⁰. Continuous time in years from the baseline will be the time scale. An interaction term between treatment assignment and time will be used to test if rates of cognitive change differ by treatment assignment. Model fit will be assessed with residual plots and other statistics (Akaike Information Criterion, Bayesian Information Criterion, etc.). The primary analysis may include adjustments for the baseline hearing loss, ARIC vs de novo status, center, age, sex, education, and APOE ϵ 4 alleles.

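### Sensitivity analysis (b) assumes that phone testing shifts both arms equally; a second fit with a treatment-by-mode term would show whether its result depends on that assumption

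*SAP*

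**What the plan says.** SAP 7.4 opens its list with "Additional analyses of the primary outcome may include, but are not limited to". Item (b), repeated in Protocol 12.2, puts the ten in-person and six phone tests into one factor model, scales the result to the in-person metric, and then specifies: "Mode of data collection (in-person, phone) will be included in the analytic model as a covariate". Neither document adds a treatment-by-mode term or an arm-specific calibration.

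The tested quantity is set in SAP 7.3: "An interaction term between treatment assignment and time will be used to test if rates of cognitive change differ by treatment assignment". The primary outcome does not use phone scores: "Factor scores are generated for each participant at each in-person assessment using a measure harmonization and item banking approach" (SAP 7.2).

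On timing, SAP 7.1 says that "a modified six-test phone-based neurocognitive assessment was administered beginning in July 2020" and that "In-person administration of the original ten tests resumed in June 2021". Randomization had ended on 25 October 2019 (SAP 9), so every phone score is a follow-up score.

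On content, Protocol 19.2.2 says of the oral CERAD list that it "is used in lieu of the visual Delayed Word Recall test". Trails A and B also become oral (Protocol 19.2.4-19.2.5). In person, instructions are both spoken and shown (Protocol 7.2.1).

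On treatment, the hearing arm is fitted with aids, and Protocol 9.1 adds: "Each participant will receive at least one HAT, depending on his or her specific goals, and outcomes of hearing aid use" (HAT is a hearing assistive technology). SAP 5.1 counts, at 6 October 2021, 46 controls using aids (9.4%) and 8 hearing-arm participants not using them (1.6%).

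**The concern.** A mode main effect removes a phone shift that both arms share. It cannot remove a shift that differs between them. Here the randomized treatment is hearing itself, and the alternative mode depends on hearing an examiner over the telephone, so equal shifts are an assumption that deserves a check. Phone scores occur only after randomization, so an arm difference in the phone effect is partly confounded with treatment-by-time, the term being tested.

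At stake is what (b) can tell the reader. It is the only listed analysis of global decline that uses the phone battery's factor score; the imputation model in SAP 7.3 lists in-person factor scores. If the phone were harder for controls, (b) would lean toward benefit. If it were harder for the hearing arm, (b) would lean the other way. In either case its agreement or disagreement with the primary result would be hard to interpret.

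**Working it through.** **Yardstick.** The planned 3-year difference is 3 × (0.08 − 0.052) = 0.084 SD (SAP 5.1). To confirm that it matches the plan's power: 850 randomized and 27.1% attrition give 425 × 0.729 = 309.8 per arm; 15% crossover gives 0.084 × 0.85 = 0.0714; the SD of 3-year change is 0.27 (Protocol 12.1). The standard error is 0.27 × √(2/309.8) = 0.0217, and 0.0714/0.0217 = 3.29, so two-sided power at 0.05 is 90.9%. The protocol states 90%.

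**Difference in aid use.** (100 − 1.6) − 9.4 = 89.0 percentage points.

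**How a differential phone effect reaches the treatment term.** Let A = 1 for the hearing arm, t = years, M = 1 for phone. Analysis (b) fits

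E(Y) = β0 + β1·A + β2·t + β3·A·t + β4·M.

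Suppose there is no treatment effect and the phone lowers control scores by d more than hearing-arm scores. Taking the control-only case,

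−d(1 − A)M = −(d/2)M + d(A − ½)M.

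With 1:1 allocation β4 absorbs the first part. The second has no term of its own and projects partly onto A·t. Write the resulting 3-year bias, 3 × β3, as λ·d.

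**Calendar and variance inputs.** From the documents: enrolment November 2017 to 25 October 2019, N = 977, annual visits, in-person suspension from mid-March 2020, phone battery from July 2020, in-person return in June 2021, and an in-person Year 3 component at least 3 months after the phone component. Assumed: uniform accrual, no attrition, no battery between mid-March and July 2020, in-person catch-up within 6 months of mid-June 2021, random intercept SD 0.95, random slope SD s, and residual SD r set so that 9s² + 2r² = 0.27². About 32% of follow-up assessments are then by phone.

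**Results (generalized least squares).**

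| Slope SD | Residual SD | λ, split Year 3 visit | λ, no in-person Year 3 visit |
|---|---|---|---|
| 0.03 | 0.180 | 0.229 | 0.360 |
| 0.05 | 0.159 | 0.222 | 0.361 |
| 0.07 | 0.120 | 0.213 | 0.362 |
| 0.08 | 0.087 | 0.208 | 0.363 |

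In every row the mode coefficient is about −0.5d. A phone shift equal in both arms gives zero bias. Adding A·M to the model also gives zero bias.

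| Assumed arm difference d | Bias, split (λ ≈ 0.22) | % of 0.084 | Bias, no split (λ ≈ 0.36) | % of 0.084 |
|---|---|---|---|---|
| 0.05 SD | 0.011 | 13 | 0.018 | 21 |
| 0.10 SD | 0.022 | 26 | 0.036 | 43 |
| 0.20 SD | 0.044 | 52 | 0.072 | 86 |

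If the shift belongs to people without aids rather than to an arm, a penalty p per non-user gives d = (0.906 − 0.016) × p = 0.89p. With p = 0.10 and split visits the bias is 0.22 × 0.089 = 0.020 SD.

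**Effect on the test in (b).** With split visits and no true effect, the two-sided 5% test would reject in 23-32% of trials at d = 0.10. With larger residual noise (SD 0.2-0.3, slope SD 0.09) the figure is 12-15%.

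**Price of the interaction.** The standard error of the 3-year contrast goes from 0.0155-0.0169 to 0.0158-0.0170 with split visits (about 1-2%), and from 0.0166-0.0171 to 0.0174-0.0175 without (about 2-5%).

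**The case against.** A reader might infer that hearing-arm participants take the phone battery with aids and streaming devices while controls struggle without them, so that (b) would turn a control penalty into a treatment effect. The documents do not support that.

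- No section says that aids or assistive devices are used on test calls. Protocol 10 mentions a general testing standard that people use their everyday sensory aids, but only when explaining why certain blinding designs were rejected. SAP 9 expects that some participants used their aids less during the quarantine.
- No phone penalty is reported for either arm.
- A telephone version of the Ensuring Speech Understanding check comes first in the phone battery (SAP Table 7.1). Protocol 7.2.2 gives its purpose as keeping hearing loss from confounding the tests. The action on failure is in the manual of procedures, which is not available here.
- The battery is voice-only, but few of its tests depend on hearing the items. Oral Trails and the two fluency tests are spoken production. Only the CERAD list and digit span rest on heard items, and digit span is heard in person too. If all six tests had equal weight (an assumption), 0.1 SD on the whole score would need 0.1 × 6/2 = 0.3 SD on each of those two.
- Analysis (b) is optional, and (c) and (d) also address missing data.

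All of this stands. It makes a large differential shift less likely and leaves its sign open. It does not show that the shift is zero, and (b) as written has no term that would reveal one.

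There is also an objection to the remedy. The phone battery ran only from July 2020 to June 2021, so phone mode and pandemic period coincide. SAP 9 anticipates a smaller intervention effect in that period, and a treatment-by-mode term would absorb that real change as well. This is why the term should not simply replace the main-effect model.

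**Conclusion.** The point holds as a cheap improvement to an optional analysis. Analysis (b) assumes equal phone shifts in two arms that differ by 89 percentage points in aid use, and gives no means of checking this. If the shifts differ, about 21-23% of the difference enters the 3-year contrast of (b), or about 36-37% where no in-person Year 3 visit follows. For assumed differences of 0.05-0.2 SD and split visits, that is about 0.011-0.044 SD against 0.084 SD.

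The shares rest on the assumed calendar and a linear mixed model, so they are approximate. The size and direction of the arm difference are assumptions throughout. The documents do not support a claim that (b) will show a false benefit, nor any doubt about the primary result, which uses in-person scores.

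**What to change.** In SAP 7.4(b) and Protocol 12.2(b), keep the model with the mode main effect and add a second fit that includes a treatment-by-mode interaction. Report the treatment-by-time estimate and confidence interval from each, together with the interaction estimate and its confidence interval. State that phone mode coincides with July 2020 to June 2021.

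If the two treatment-by-time estimates agree, the result of (b) does not hinge on equal phone shifts. If they differ, (b) alone cannot separate an arm-specific phone effect from a change in treatment effect during the pandemic, and the report should say so.

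The cost is one model term, a sentence or two in each document, and no new data. In the second fit the standard error of the 3-year contrast rises by about 0-2%, or up to about 5% without the split Year 3 visits.
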